We consider that a minimally important clinical effect applies for this study if results differ less than 10%. The noninferiority margin is thus set to 10%. This means that the results from study arms are considered clinically having no important differences if the results from test operation (APCI) differ less than 10% in the main outcome. We claim noninferiority for test operation if the result will be in the range less than 10% inferior result up to a trend for superior result but not statistically significant for the main outcome. If the result shows a statistically significant difference we claim superiority (or inferiority) of the test operation. If we find noninferiority based on the main outcome we may still draw conclusions about which operation should be preferred, based on results from secondary outcomes.

Data to be analyzed

All primary analyses in this study will be performed according to the intent-to-treat (ITT) principle, that is, patients will be allocated to treatment groups corresponding to their assigned treatment, even if the patient does not receive the correct treatment.

The intention-to-treat population will consist of all randomised patients who are operated with EAPE.

Per-protocol analyses are secondary and may be used if special circumstances motivate to use such. If noninferiority is to be stated we will do a per-protocol analysis in addition to the ITT analysis and if both analyses are non significant it will give more evidence of noninferiority. The per-protocol population will consist of all patients in the intent-to-treat population who have met all protocol requirements and who have successfully completed the trial up till one year.

Patient disposition

Reasons for discontinuations in the study will be compared between the 2 treatment groups. Result tables or the Consort[24] diagram will reveal the number and proportion of patients who have completed the study as well as patients that have discontinued, grouped by reason for discontinuation.

Patient characteristics

Age, gender, primary or recurrent rectal cancer will be registered when the patient is randomised via the web application and will be included in the summary reports.

Preoperative oncologic treatment and pre- and postoperative tumour classification (cTNM and pTNM) will be registered in (and retrieved from) the Swedish Colorectal Cancer Registry for Swedish patients and for patients outside Sweden a similar form with TNM data is completed via the study homepage web application by the local investigator. The pTNM classification will also be included in the summary reports.

Primary analysis

Performance in Timed-stands test (TST) measured in seconds (time) will be compared between study arms at 6 months from the operation and tested with appropriate statistical tests. The proportion of patients that perform worse than the upper limit of reference values may be used as a parameter for comparison. TST reflects physical performance that is the primary outcome of the study.

Secondary analyses

1. The change of physical performance, i.e. the difference between preoperative and postoperative results in TST at 3, 6 and 12 months will be compared between study arms.
2. Primary wound healing at 3 months is categorized in subclasses (SWAS[11]) and the proportions of patients in different classes are compared between study arms.
3. Complications are categorized according to classification by Dindo-Clavien [12] and the proportions of patients in different classes are compared between study arms at 3, 6 and 12 months.

4. Ability to sit is defined in three classes and the proportions of patients in different classes are compared between study arms at 3, 6 and 12 months.
5. Pain and discomfort in gluteal region measured with VAS and analyzed with appropriate statistical methods. Comparisons will be done at 3, 6 and 12 months.
6. Quality of life is measured with EQ-5D and EORTC forms C30 and CR29 and the individual responses are calculated to a health utility index using an appropriate table/tariff for the general population[25, 26] Spot measures at 3, 6 and 12 months and differences between pre-treatment and postoperative measurements will be compared.
7. The proportion of patients that present local recurrence during the study period will be compared between study arms.

Subgroup analyses

1. Costs of surgical treatments and QALYs gained are calculated for a subpopulation of the study population. Registration of parameters needed for the health economic calculations is optional for the participating centres and the subpopulation will be included only from centres that collect health economic data in their computer systems. Costs of surgical treatments including surgical complications up till 12 months will be calculated according to health economic standards and QALYs gained will be compared between study arms.
2. Two different rehabilitation programmes will be used for study patients and every participating centre must decide which of the programmes to use. The centre must stay to the chosen rehabilitation programme throughout the study. A subgroup analysis will be performed with the aim to reveal if the rehabilitation program has an impact on the main and secondary outcomes.

Safety analyses

An independent observer will be appointed with the task to contact each centre yearly and ask for unforeseen adverse events and problems. If severe adverse events occur the PI and the independent observer have the responsibility to decide whether the study can continue or should be stopped.

All safety analyses comparing the treatment groups will be performed based on the intent-to-treat population. All statistical tests of safety will be conducted at a two-sided alpha-level of 0.05. The safety analysis variables include, but are not restricted to:

- Postoperative mortality in 30 days
- Postoperative complications Grade IIIb or higher according to Dindo-Clavien
- Proportions of serious adverse events

Interim analyses

Interim analyses will be performed only if the study inclusion period exceeds 5 years. Safety analyses are exceptions that are performed whenever proposed by the independent observer.

Informed consent, ethical review and regulatory considerations

Informed consent

The informed consent document with study information will be used to explain in simple terms to patients what participation in the study means for the patient. The patient will get information of the risks, benefits and the alternatives available.

It is the investigators responsibility to see that informed consent is obtained from each patient or legal representative before enrolment in the study. The informed consent document must be signed and dated and finally stored in archive at each participating centre. The signed document may also be photo-scanned to an electronic document and included in the hospital electronic patient file. Once the scan copy is secured to an electronic patient file the paper document may be destroyed.

Ethical review

The PI will apply for ethical board review at the Regional Ethical Review Board at Umeå University. The application will cover all study sites in Sweden but study sites in other countries may have to apply separately according to the local regulations. It is the site investigators responsibility in other countries than Sweden to apply and hold the local ethical review board approval for the study. After the Swedish application has been approved, the PI will provide site investigators with documentation of ethical review board approval of the protocol and informed consent document including patient information.

Regulatory considerations

This study will be conducted in accordance with the ethical principles stated in the most recent version of the declaration of Helsinki or the applicable guidelines on good clinical practice, whichever represents the greater protection of the individual.

After reading the protocol, each site investigator will sign the protocol signature page, see Appendix last page, and return it to the PI.

References

1. Miles, W.E., *A method of performing abdominoperineal excision for carcinoma of the rectum and of the terminal portion of the pelvic colon*. Lancet, 1908. **2**: p. 1812-1813.
2. Davies, M., et al., *Local recurrence after abdomino-perineal resection*. Colorectal Dis, 2009. **11**(1): p. 39-43.
3. Heald, R.J., et al., *Abdominoperineal excision of the rectum--an endangered operation*. Norman Nigro Lectureship. Dis Colon Rectum, 1997. **40**(7): p. 747-51.
4. Thirion, P., et al., *Survival impact of chemotherapy in patients with colorectal metastases confined to the liver: a re-analysis of 1458 non-operable patients randomised in 22 trials and 4 meta-analyses*. Meta-Analysis Group in Cancer. Ann Oncol, 1999. **10**(11): p. 1317-20.
5. Marr, R., et al., *The modern abdominoperineal excision: the next challenge after total mesorectal excision*. Ann Surg, 2005. **242**(1): p. 74-82.

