Form P1: Physiotherapist, pre-treatment	26
Form P2: Physiotherapist, test form	26
Form P3: Physiotherapist or study nurse, postoperative	27
NEAPE uppgifter om RT och OP.....	27
Informerat samtycke	29
Protocol signature	30

Introduction

Abdominoperineal excision (APE) of the rectum is the potentially curative operation for rectal carcinomas too low for reconstructive surgery, especially if the levator and sphincter musculature is infiltrated[1]. Preoperative chemo radiotherapy is often used.

The local recurrence rate after APE has been reported to be from 5% up to 47% [2-4]. Consequently, much interest has focused on improved surgical technique, in which the levator musculature is included in the excision by division laterally close to the pelvic wall, creating a cylindrical specimen, as described already by Miles[1, 5, 6]. Encouraging oncological results have been reported [2, 7]. This enlarged operation, when the levator musculature is excised en bloc with the rectum, creates a large defect. Primary closure is often not possible, and reconstruction with prosthetic material or a myocutaneous flap is necessary to avoid a perineal hernia. Implantation of a collagen sheet has shown preliminary good results[8].

Reconstruction with a gluteus maximus myocutaneous flap has the advantages to a trans-abdominal flap of not damaging the abdominal wall, as well as not implanting foreign material. Therefore we have proposed that this study should only use a gluteus maximus myocutaneous flap. Promising results with low local complication rate have recently been reported [7]. However, the gluteus maximus muscle is a strong hip extensor and important for posture and balance. As far as we know, the functional outcome and quality of life (QoL) after this method of reconstruction have not been compared to alternative techniques earlier.

The current study is by definition a comparative effectiveness research project.

Objectives

Primary objective

To show if EAPE can be performed with APCI resulting in better outcome in physical performance compared to reconstruction with unilateral GMF (current standard).

To show superiority or noninferiority of test operation (APCI).

Secondary objectives

1. To study which of the techniques result in:
 - a) better primary wound healing
 - b) less late complications including inability to sit, pain and discomfort in gluteal region

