4. The reconstruction of lesser pelvis floor with APCI will result in better quality of life than the GMF operation.
5. The reconstruction of lesser pelvis floor with APCI will result in lower costs of treatment and more QALYs gained than the GMF operation.
6. The local recurrence rate is not related to the method of reconstruction of lesser pelvis

Noninferiority hypothesis:

1. The reconstruction of lesser pelvis floor with APCI will result in clinically equivalent physical performance provided that results will be within defined noninferiority margins, see below.

Noninferiority margin:

The noninferiority margin is set to 10%. Interpretation, see section Data analysis methods.

Summary of study design

The study is multi-centre, prospective randomised and with parallel assignment. Centres that treat locally advanced rectal cancers with the extended abdominoperineal excision of rectum (EAPE)[7] can participate provided that:

1. the operative technique is standardized according to this protocol, see section Surgical methods
2. the centre/unit has resources for examinations of participants by a physiotherapist or a nurse
3. the centre/unit has one investigator in charge of the study locally
4. the centre/unit has an operative volume that enables at least 6 patients to be included/randomised during the anticipated three year study phase for inclusions

Centres that do not operate the rectal cancers included in this study can participate by arranging the preoperative examination and physical tests as well as follow-up of patients that are referred to other centres for the operation. In these cases the operating centre cares for the randomisation, operation and start of postoperative rehabilitation while the study follow-up and final rehabilitation can be completed at the patients' primary referral

hospital. The primary referral hospital needs a site investigator in charge of study patients just like centres that do the operations.

Patients with primary or recurrent cancers of rectal origin can be included but individual patients can be included only once. Concomitant therapies are allowed and preoperative or postoperative radiation therapy and/or chemotherapy may be given or not according to local multidisciplinary team (MDT) decisions.

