Once per year an independent advisor that together with the PI has the authority to stop the study if serious unexpected safety issues can be observed will evaluate the collected data of clinical adverse events. If the independent advisor and the PI make a decision to stop the study, the decision must be written and motivated in detail and distributed to all participating centres without delay.

Quality control and quality assurance

To ensure accurate and reliable data the study administration will do the following:

- Provide instructional material to the study sites, as appropriate (manual for physical examination etc.)
- Update study homepage at www.norrandskirurgi.se with relevant information and study material
- Start-up training, meeting with investigators
- Be available for consultation
- Conduct quality review of database (a monitor may be sent to participating centres)

Data analysis methods

Sample size

The sample size is calculated with the following assumptions:

- Estimated proportion of patients with low performance in TST with GMF 63%
- Estimated proportion of patients with low performance in TST with APCI 30%
- Estimated loss of data/cases 20% (mortality etc.)

The calculation gives that a total of 108 patients (54 patients in each study arm) are needed with 90% power and a significance level of 0.05 (alpha).

If the anticipated three-year inclusion phase of the study is too short for including 108 patients an alternative power calculation with 80% power will be used instead and the study will include a total of 80 patients only before the inclusion phase will be closed.

Interpretation of noninferiority

The noninferiority margin for the study is set on the basis of a minimally important clinical effect, which is a subjective judgement of the best expertise available. This approach remains the only alternative since there are no historical placebo controlled trials in the field for guidance and for practical reasons such trials are not possible to conduct.

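### The primary objective includes noninferiority, but the 108 (or 80) patients are sized for superiority only, and the stated claim rule would not support a noninferiority conclusion

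*Protocol*

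**What the plan says.** Under Objectives, Primary objective, the protocol sets out "To show superiority or noninferiority of test operation (APCI". A separate noninferiority hypothesis follows under Hypotheses of study, and the next section fixes the margin: "The noninferiority margin is set to 10" per cent.

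The only sizing is under Data analysis methods, Sample size. Its inputs are:

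- "Estimated proportion of patients with low performance in TST with GMF 63" per cent
- "Estimated proportion of patients with low performance in TST with APCI 30" per cent
- "Estimated loss of data/cases 20% (mortality etc".

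The result is stated as "The calculation gives that a total of 108 patients (54 patients in each study arm) are needed". The power attached to that size is 90%, and alpha is 0.05. If three years of inclusion do not suffice, the trial closes at 80 patients with 80% power.

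Interpretation of noninferiority says when the claim is made: the APCI result is worse by under 10%, or tends to be better, and the difference is not significant. No confidence limit is mentioned. That section then lets secondary outcomes decide which operation to prefer. Data to be analyzed adds a per-protocol analysis and counts two non-significant results as stronger evidence of noninferiority.

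Primary analysis compares TST in seconds at 6 months. The proportion beyond the reference limit is an optional alternative.

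**The concern.** The objective has two routes to success, and the protocol gives one size and one power. The inputs to that size describe a 33-point advantage for APCI, so they speak only to superiority. The noninferiority route matters when the two operations perform about alike, and the protocol gives no power for that case.

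The claim rule makes this worse. It rests on the observed difference and on a lack of significance, and a small trial can produce both when APCI is worse by the full margin. At stake is a noninferiority statement on the main outcome that the data cannot carry, followed by a choice of operation on secondary outcomes that relies on it.

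**Working it through.** **Inputs.** From Sample size: 63% (GMF), 30% (APCI), alpha 0.05, 20% loss, 54 per arm or 40 per arm in the fallback. From Noninferiority margin: 10%. Assumptions:

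- Superiority is tested two-sided; the protocol states sidedness for safety tests only.
- Noninferiority is judged by a two-sided 95% limit.
- The margin means 10 percentage points on the proportion, unless noted otherwise.

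**1. The plan's own figures.** For two proportions with unpooled variance:

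n = (0.63×0.37 + 0.30×0.70) × (z₀.₉₇₅ + z_power)² / 0.33²

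- 90% power: 0.4431 × (1.960 + 1.282)² / 0.1089 = 42.75, so 43 per arm. 43/0.8 = 53.75, so 54 per arm and 108 in total.
- 80% power: 0.4431 × (1.960 + 0.842)² / 0.1089 = 31.94, so 32 per arm. 32/0.8 = 40 per arm and 80 in total.

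Both match exactly. They are superiority sizes, and the margin appears nowhere in them.

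**2. Noninferiority power on the proportion.** Power = Φ((margin + true advantage of APCI)/SE − 1.96).

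- Equal rates of 63%, 43 per arm: SE = √(2×0.63×0.37/43) = 0.104. 0.10/0.104 = 0.960. Φ(0.960 − 1.96) = 15.9%. The half-width of the 95% interval is 1.96 × 0.104, about 20 points, or twice the margin.
- Same, 32 per arm: SE = 0.121, power 12.9%.
- Same, with no loss at all (54 per arm): 18.8%.
- Equal rates of 30%, 43 per arm: 17.2%.
- Margin read as relative (0.10 × 63% = 6.3 points), equal rates of 63%, 43 per arm: 8.8%.

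The figure depends on the true APCI rate. With GMF at 63% and 43 per arm:

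| True APCI rate | Noninferiority power |
|---|---|
| 63% | 16% |
| 60% | 24% |
| 53% | 47% |
| 43% | 81% |
| 30% (design) | 99% |

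**3. Noninferiority power in seconds.** The documents give neither mean nor SD. With a margin of 10% of the mean, equal means and 43 per arm, SE = CV × √(2/43) = 0.2157 × CV, where CV is the SD as a fraction of the mean.

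- Assumed CV 0.20: SE 0.0431, Φ(2.318 − 1.96) = 64%.
- Assumed CV 0.30: SE 0.0647, Φ(1.546 − 1.96) = 34%.
- Assumed CV 0.40: SE 0.0863, Φ(1.159 − 1.96) = 21%.

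90% power would need a CV of at most 0.10/(3.2416 × 0.2157) = 0.143, before any baseline adjustment.

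**4. The claim rule as written.** Take it on the proportion with 43 per arm: observed APCI rate less than 10 points worse, and not significantly better.

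- Equal rates of 63%: Φ(0.960) − 0.025 = 0.832 − 0.025 = 81%.
- APCI truly at 73%: SE = √((0.63×0.37 + 0.73×0.27)/43) = 0.100. P(observed difference < 0.10) = 50%, of which about 0.2 points are significantly better, leaving 49.8%.

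A 95% limit would hold the second figure to about 2.5%.

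**The case against.** Several counter-arguments have weight.

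- *The only hypothesis labelled primary is superiority, and 63% against 30% stands next to the stated power.* A careful reader would see what was sized. This softens the point, but the primary objective still names noninferiority, and nothing says that the power leaves it out.
- *The 16% is on the optional scale.* This stands. Primary analysis puts seconds first, and there the result depends on an SD that the protocol does not give. Preoperative TST is collected, and adjusting for it is neither specified nor excluded. With an assumed CV of 0.20 and an assumed baseline correlation of 0.7, the effective CV is 0.20 × √(1 − 0.49) = 0.143, which is the 90% threshold.
- *The 16% assumes equality.* This stands too. Power rises if APCI is better, and at the design effect it is about 99%, where superiority would be expected anyway. Equality is nevertheless the natural case for a noninferiority claim.
- *The stated rule needs no confidence limit.* True as the text reads, but step 4 shows that the rule then offers little protection against a false claim.

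A reader might infer that the trial would almost always be inconclusive on noninferiority. The documents do not support that. In seconds, power could be 64% or more under plausible assumptions, and under the rule as written the likelier failure is an unsupported claim. Nor is the sample size miscalculated, since both stated totals reproduce.

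**Conclusion.** The point holds as a mismatch between objective and sizing. The stated 90% and 80% apply to superiority at a 33-point difference, and noninferiority has no stated power.

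On the proportion, noninferiority power is about 16% (13% in the fallback). This requires equal true rates of 63%, 43 (32) evaluable per arm, a two-sided 95% limit and a margin of 10 percentage points. It should not be quoted without those conditions. In seconds only a range can be given, about 21% to 64% for assumed SDs of 40% down to 20% of the mean, unadjusted.

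The literal claim rule, evaluated on the proportion, declares noninferiority about 81% of the time under equality and about 50% of the time when APCI is worse by the whole margin. A declaration on that basis would be unsupported.

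**What to change.** No patients need be added. Sizing the proportion for noninferiority under equality at 63% would take (1.960 + 1.282)² × 0.4662/0.10² = 490 evaluable per arm, or 613 per arm and 1,226 in total after 20% loss, which is out of proportion to this trial. Change the wording in four places:

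1. **Sample size.** State that the 90% and 80% apply to superiority only and that the trial is not powered for noninferiority. Give the conditional figure with its scale and assumptions, and say that power in seconds depends on an SD not yet specified.
2. **Primary objective.** Remove the noninferiority alternative, which brings it into line with the primary hypothesis.
3. **Noninferiority hypothesis and margin.** Align the hypothesis with the revised objective, and say whether the 10% is absolute or relative and whether it refers to the proportion or to seconds.
4. **Interpretation of noninferiority.** Replace the rule: noninferiority is claimed only if the 95% confidence limit for the difference, on the named scale, excludes the margin. Otherwise report the estimate with its interval. Apply the same criterion to the per-protocol analysis under Data to be analyzed, in place of non-significance.

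The cost is a protocol amendment and a less favourable stated ambition. No procedures change.
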